8.2.1.2.3. Sensitivity Analysis: Imputation of PP population from LEAP PP

LEAP PP Participants who participated in LEAP Trio but have a missing peanut allergy determination for LEAP Trio at V144 according to the definition in section 8.2.1.1, or who did not participate in LEAP Trio will have the peanut allergy status at V144 imputed.

LEAP PP Participants with a missing peanut allergy determination at V144 will have their peanut allergy status from the LEAP On primary endpoint for peanut allergy status at V72 carried forward (via LOCF) as their V144 peanut allergy status. LEAP PP Participants with a missing peanut allergy status at V72 will have their peanut allergy status from the LEAP primary endpoint for peanut allergy status at V60 carried forward (via LOCF) as their V144 peanut allergy status.

The same statistical methodology in section 8.2.1.2 will be repeated for this sensitivity analysis to compare the rate of peanut allergy between LEAP Consumers and LEAP Avoiders at V144.

8.2.1.2.4. Sensitivity Analysis: Imputation of PP population from LEAP PP with Transient Allergy Rate

LEAP PP Participants who participated in LEAP Trio but have a missing peanut allergy determination for LEAP Trio at V144 according to the definition in section 8.2.1.1, or who did not participate in LEAP Trio will have their peanut allergy status at V144 imputed.

LEAP PP Participants with peanut allergy status at V72

For the LEAP Participants with a peanut allergy status at both V72 and V144, if there are any participants whose peanut allergy status changes from V72 to V144, the percentage of participants who change from allergic to tolerant (%A72→T) and the percentage of participants who change from tolerant to allergic (%T72→A) will be calculated.

For LEAP PP Participants with a missing peanut allergy determination at V144 and a peanut allergy status of allergic at V72 (NumPPA72), [NumPPA72 * %A72→T] participants will be randomly selected to be imputed as tolerant at V144 and the remaining participants in NumPPA72 will be imputed as allergic at V144.

For LEAP PP Participants with a missing peanut allergy determination at V144 and a peanut allergy status of tolerant at V72 (NumPPT72), [NumPPT72 * %T72→A] participants will be randomly selected to be imputed as allergic at V144 and the remaining participants in NumPPT72 will be imputed as tolerant at V144.

LEAP PP Participants with missing peanut allergy status at V72

For the LEAP Participants with a peanut allergy status at both V60 and V144, if there are any participants whose peanut allergy status changes from V60 to V144, the percentage of participants who change from allergic to tolerant (%A60→T) and the percentage of participants who change from tolerant to allergic (%T60→A) will be calculated.

For LEAP PP Participants with a missing peanut allergy determination at V144, a missing peanut allergy status at V72 and a peanut allergy status of allergic at V60 (NumPPA60), [NumPPA60 * %A60→T] participants will be randomly selected to be imputed as tolerant at V144 and the remaining participants in NumPPA60 will be imputed as allergic at V144.

For LEAP PP Participants with a missing peanut allergy determination at V144, a missing peanut allergy status at V72 and a peanut allergy status of tolerant at V60 (NumPPT60), [NumPPT60*%T60→A] participants will be randomly selected to be imputed as allergic at V144 and the remaining participants in NumPPT60 will be imputed as tolerant at V144.

The same statistical methodology in section 8.2.1.2 will be repeated for this sensitivity analysis to compare the rate of peanut allergy between LEAP Consumers and LEAP Avoiders at V144.

8.2.1.2.5. Sensitivity Analysis: Imputation of ITT population from LEAP ITT

LEAP ITT Participants who participated in LEAP Trio but have a missing peanut allergy determination for LEAP Trio at V144 according to the definition in section 8.2.1.1, or who did not participate in LEAP Trio will have the peanut allergy status at V144 imputed.

LEAP ITT Participants with a missing peanut allergy determination at V144 will have their peanut allergy status from the LEAP On primary endpoint for peanut allergy status at V72 carried forward (via LOCF) as their V144 peanut allergy status. LEAP ITT Participants with a missing peanut allergy status at V72 will have their peanut allergy status from the LEAP primary endpoint for peanut allergy status at V60 carried forward (via LOCF) as their V144 peanut allergy status.

The same statistical methodology in section 8.2.1.2 will be repeated for this sensitivity analysis to compare the rate of peanut allergy in the LEAP ITT population between LEAP Consumers and LEAP Avoiders at V144.

8.2.1.2.6. Sensitivity Analysis: Imputation of ITT population from LEAP ITT with Transient Allergy Rate

LEAP ITT Participants who participated in LEAP Trio but have a missing peanut allergy determination for LEAP Trio at V144 according to the definition in section 8.2.1.1, or who did not participate in LEAP Trio will have their peanut allergy status at V144 imputed, using the same imputation methods specified in section 8.2.1.2.4.

The same statistical methodology in section 8.2.1.2 will be repeated for this sensitivity analysis to compare the rate of peanut allergy in the LEAP ITT population between LEAP Consumers and LEAP Avoiders at V144.

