# 9.3 SAMPLE SIZE

# **LEAP Participants**

The sample size is based on the number of children likely to be available to enroll in the study. As shown in the Figure 1 LEAP Screening, Participant and Sibling Cohorts, there are 311 LEAP avoiders and 319 LEAP consumers (total 630) potentially eligible for enrollment. In the LEAP study, the rate of peanut allergy was 3.2% among consumers and 17.2% among avoiders at 60 months of age. We assume that the rates will not change markedly between month 60 and 144. We wish to detect a difference between the groups that are similar to that detected at 60 months. 88.5% of those potentially eligible enrolled in the follow on LEAP-On Study. We assume a lower percentage of those potentially eligible will enroll in this study.

For example, if 80% of those potentially eligible enroll, the true rate of allergy among LEAP consumers at 144 months is 6%, and the true rate of allergy among LEAP avoiders at 144 months is 15%, there is 91% power to detect a difference with a two-sided type I error of 0.05 between the groups. If only 70% enroll and other assumptions remain constant, there would be about 87% power to detect a difference.

Other examples are shown in Figure 3.

Three possible recruitment rates are shown in the left, middle and right panels. In each panel, the power to detect a difference, with a two-sided type I error of 0.05, between groups is shown on the vertical axis for different assumptions regarding the true underlying allergy rates in the consumer and avoider groups at month 144. In each panel contour lines display rates in consumers of 2%, 4%, 6%, 8% and 10% while the horizontal axis displays a range of rates in avoiders of 10 to 25%

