8.2.1.2. Primary Analysis: Between-group comparison

The main comparison for the LEAP Participant primary endpoint is the rate of peanut allergy between LEAP Consumers and LEAP Avoiders at V144 in the ITT population. This comparison will be made by an unadjusted logistic regression model at the 0.05 level of significance. This comparison evaluates whether the consumption of peanut starting in infancy induces long-lasting tolerance to peanut.

The same statistical methodology will be repeated for the LEAP Participants in the PP population.

The same statistical methodology will be repeated in the ITT and PP populations, separately, within each stratum from the LEAP Study randomization (skin prick test (SPT)-positive and SPT-negative groups from the LEAP Study).

Additional logistics regression models will be performed to adjust for potential confounders, such as age, gender, ethnicity, family history and other allergic comorbidities

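### The carried-forward sensitivity analyses in SAP 8.2.1.2.5 and 8.2.1.2.3 assume the persistence that Visit 144 is meant to test, so they are not a valid check on it

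*SAP*

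**What the plan says.** SAP 8.2.1.2 compares peanut allergy at V144 between LEAP consumers and avoiders: "This comparison will be made by an unadjusted logistic regression model at the 0.05 level of significance". Its stated purpose is persistence: "This comparison evaluates whether the consumption of peanut starting in infancy induces long-lasting tolerance to peanut". Under SAP 8.2.1.1, children with no challenge, no qualifying peanut consumption and no input for the prediction model are left out of this primary analysis.

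Six sensitivity analyses then fill in missing V144 status and repeat the same regression.

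- **Carried forward.** In 8.2.1.2.5 (LEAP ITT) and 8.2.1.2.3 (LEAP PP), V72 status, or V60 status where V72 is missing, is "carried forward (via LOCF) as their V144 peanut allergy status". Both explicitly include LEAP children who did not take part in Trio. 8.2.1.2.1 carries V72 status only, and its text does not mention children outside Trio.
- **Change-rate companions.** 8.2.1.2.2, 8.2.1.2.4 and 8.2.1.2.6 switch a random subset of the filled values, using the percentages observed to move between allergic and tolerant. These percentages are defined over LEAP participants with both statuses. No split by arm is given.

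**The concern.** Carrying a V72 or V60 status forward asserts that no filled child has changed since age 5 to 6. Whether children have changed is what V144 was set up to learn. The arms already differed widely at those visits: 18.6% against 4.8% at V72 (Protocol 1.1) and 17.2% against 3.2% at V60 (Protocol 9.3). Each filled value therefore imports the old difference into a test labelled V144, always in favour of consumers and in proportion to the share filled.

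At stake is how the robustness tables are read. If they agree with the primary result, a reader will count that as independent support, although part of the agreement is older data under a new label. If protection had faded, they could still show a significant difference.

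**Working it through.** **1. The plan's own power figures.** Protocol 9.3 states that "there are 311 LEAP avoiders and 319 LEAP consumers (total 630) potentially eligible for enrollment". With 80% enrolled, 6% allergic among consumers and 15% among avoiders, "there is 91% power to detect a difference with a two-sided type I error of 0.05 between the groups". It adds: "If only 70% enroll and other assumptions remain constant, there would be about 87% power to detect a difference". Pooled-variance formula: power = Φ[(0.09 − 1.96·SE0)/SE1].
- 80% enrolled (249 avoiders, 255 consumers): SE0 = 0.02725, SE1 = 0.02708, power 91.2%.
- 70% enrolled (218, 223): SE0 = 0.02913, SE1 = 0.02894, power 87.2%.

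Both reproduce, so the arm sizes and the 20% and 30% shortfalls used below are the plan's own.

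**2. Assumptions the documents do not supply.** No arm difference at V144, with a common rate of 12% (range 8% to 15%); the same share m missing in both arms; missing children having the arm-average earlier rate. LEAP ITT counts by arm are not printed. I use 319 and 311 (total 630); Protocol 1.1 uses 628 as its denominator, which is immaterial here.

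**3. Expected rates after filling.** Filled rate = (1 − m) × 12% + m × earlier rate. With V72 values:
- m = 10%: avoiders 10.8 + 1.86 = 12.66%; consumers 10.8 + 0.48 = 11.28%; gap 1.38 points.
- m = 20%: 9.6 + 3.72 = 13.32%; 9.6 + 0.96 = 10.56%; gap 2.76 points.
- m = 30%: 8.4 + 5.58 = 13.98%; 8.4 + 1.44 = 9.84%; gap 4.14 points.

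The gap is m × 13.8 points (m × 14.0 with V60 values). The true gap is zero.

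**4. Rejection rate, 8.2.1.2.5.** Worked case, m = 30%: OR = (9.84/90.16)/(13.98/86.02) = 0.67, log OR −0.398. Expected allergic counts are 43.5 of 311 and 31.4 of 319, so SE = √(1/43.5 + 1/267.5 + 1/31.4 + 1/287.6) = 0.249 and the mean z is −1.60. Rejection ≈ Φ(1.60 − 1.96) = Φ(−0.36) ≈ 36%. Simulation of the Wald test (200,000 trials per setting, common rate 12%):

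| Missing | V72 fill | V60 fill | Median OR |
|---|---|---|---|
| 0% | 5% | 5% | 1.00 |
| 10% | 8% | 8% | 0.87-0.88 |
| 20% | 18% | 19% | 0.76-0.77 |
| 30% | 36% | 38% | 0.66-0.67 |

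At 20% and 30% missing almost every rejection favours consumers. Over common rates of 8% to 15% the range is about 16% (20% missing, 15% rate, V72 fill) to 46% (30% missing, 8% rate, V60 fill).

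**5. 8.2.1.2.1.** If only enrolled children are filled and 2% to 5% of them lack a determination (an assumption), rejection is about 5% to 6%.

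**6. The companions, read as pooled over arms.** Take the smallest changes that bring both arms from V72 to 12%. Among avoiders, 1 − 12/18.6 = 35.5% of allergic children become tolerant. Among consumers, (12 − 4.8)/95.2 = 7.6% of tolerant children become allergic. Pooling, with arms taken as equal in size, gives 6.6/23.4 = 28.2% and 7.2/176.6 = 4.1%. Filled avoiders are then 18.6 × 0.718 + 81.4 × 0.041 ≈ 16.7% allergic, and filled consumers 4.8 × 0.718 + 95.2 × 0.041 ≈ 7.3%. A gap of about 9 points survives where the truth is none. Simulated rejection is about 10% at 20% missing and 17-18% at 30%. With arm-specific percentages it is 6-8%; the remaining excess reflects a single imputation analysed as observed data.

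**The case against.** The strongest defence is that nothing confirmatory rests on these tables. The primary analysis contains no carried-forward values. Under step 4 with V72 fill, the primary and carried-forward tests both reject in only about 2.4% of trials, so most false alarms would appear beside a null primary result and look discordant. The SAP also examines fading elsewhere: the companions, the paired tests in consumers (8.2.1.3), status across V60, V72 and V144 (8.2.1.4), and earlier characteristics of those who did and did not join Trio (6.2). The null is severe, since consumers must rise from 4.8% to 12% while avoiders fall from 18.6% to 12%. At the planning rates of 6% and 15% the carried-forward gap would be 0.8 × 9 + 0.2 × 13.8 = 10.0 points at 20% missing, an exaggeration but not a reversal.

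Most of this stands and limits the point. A reader might infer that the trial's own false-positive rate is 18% to 38%. The documents do not support that, because those rates belong to a sensitivity analysis. Nor do they support treating all three carried-forward analyses alike: 8.2.1.2.1 lacks the clause on children outside Trio, and PP arm sizes are not given. The companion figures depend on reading the percentages as pooled, which is the natural reading but is not stated outright.

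What the defence does not restore is the purpose of 8.2.1.2.5 and 8.2.1.2.3. A check that leans towards persistence by construction cannot corroborate persistence. The tests in 8.2.1.3 are within consumers and require a determinate V144 challenge, so they do not replace a between-arm check on missing data.

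**Conclusion.** The point holds for 8.2.1.2.5 and 8.2.1.2.3 as robustness checks. Both assume the no-change hypothesis under test and shift the V144 comparison towards consumers by the missing share times about 14 points. The size is established only for 8.2.1.2.5, and only under the assumptions in step 2. It would be small if missingness were low, and partial fading was not simulated. 8.2.1.2.3 has the same flaw at an unknown size. 8.2.1.2.1 has it in principle but probably to a negligible degree, if it covers enrolled children only. The companions reduce the bias without removing it unless their percentages are arm-specific. The primary conclusion is untouched. The change should be made because agreement across these tables would otherwise overstate the evidence for lasting protection.

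**What to change.** 1. In 8.2.1.2.3 and 8.2.1.2.5, and in 8.2.1.2.1 for consistency, replace carrying forward with multiple imputation of V144 status within each arm. Use V72 status (else V60), earlier peanut SPT, peanut IgE and Ara h2 as predictors, and combine by Rubin's rules. Specify a penalised or reduced model in case allergic consumers are too few (13 of 270 at V72). State in 8.2.1.2.1 whether children outside Trio are included.
2. In 8.2.1.2.2, 8.2.1.2.4 and 8.2.1.2.6, calculate the change percentages separately by arm. Repeat the random imputation, redrawing the percentages each time, and combine by Rubin's rules.
3. If a carried-forward table is kept for continuity, title it *last known status* and state that it assumes no change since V72 or V60 and is not evidence of persistence at V144.

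Cost: SAP wording and modest programming. SAP 6.2 already plans to summarise earlier SPT, peanut IgE and its components for children who did and did not join Trio, so the predictors should be in hand. Intervals will be wider, consumer cells will be sparse, and the imputation still assumes that data are missing at random given arm and the predictors.

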8.2.1.3. Secondary Analysis: New Peanut Allergy Development

The within group comparison of peanut allergy status in LEAP Consumers between V72 and V144 will allow identification and statistical evaluation of a group of children who develop peanut allergy after ad libitum consumption. This matched pre-post test allows us to explore mechanistic and immunologic differences between those who develop new peanut allergies versus those who appear to be persistently tolerant.

The peanut allergy status of the LEAP Consumers at V72 will be determined by the outcome of the peanut oral food challenge conducted in LEAP-On at V72. LEAP Consumers in the ITT population who also have a determinant outcome in the V144 peanut oral food challenge will be included in the analysis.

This comparison of the proportion of participants with peanut allergy at V72 and V144 within the LEAP Consumers group will be made using a paired (pre/post) McNemar's test at a 0.05 level of significance.

The same statistical methodology will be repeated in the comparison of the proportion of participants with peanut allergy at V60 and V144 within the LEAP Consumers group.

8.2.1.4. Exploratory Analyses of the Primary Endpoint

Change in Peanut Allergy Status over Time

The peanut allergy status in LEAP Participants will be examined across the V60, V72 and V144 time points. Immunologic outcomes and other clinical outcomes will be summarized and plotted to explore the relationships between the change or stability in the peanut allergy status over time, as well as between the LEAP Consumers and LEAP Avoiders.

Cumulative Protective Effect

The cumulative protective effect of the LEAP Study intervention on the development of peanut allergy over time will be evaluated in LEAP Participants. LEAP Participants with a peanut allergy status of allergic at any of the time points in the LEAP Studies (V60, V72 or V144) will be considered allergic. LEAP Participants with peanut allergy status of tolerant at all time points with a determinate peanut allergy status will be considered tolerant.

The prevalence of peanut allergy across the LEAP Studies will be compared between LEAP Consumers and LEAP Avoiders using a logistic regression model in all LEAP participants in the LEAP Trio ITT sample with a determinate peanut allergy status at V144 and at least one determinate peanut allergy status at V60 or V72. The same statistical methodology will be repeated in the LEAP Participants in the LEAP Trio PP sample with a determinate peanut allergy status at V144 and at least one determinate peanut allergy status at V60 or V72

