When considering IgG4 and the ratio of peanut specific IgG4:IgE, they were both significantly higher in the peanut consumption group compared to the peanut avoidance group (p<0.001) at 60 months but also 72 months (after a yearlong period of avoidance (p<0.001)). These findings therefore favour those parameters traditionally associated with tolerance. However, in the consumption group, values of peanut IgG4 had started to decrease, even at 30 months of age (when peanut consumption was ongoing). The longer-term trajectory of IgG4, and clinical relevance thereof, will become apparent after the determination of peanut allergy at 12 years of age in the LEAP Participant cohort.

Many children with peanut allergy develop concomitant sensitization and allergy to other peanut-related foods such as tree nuts and sesame. This adds an additional burden both in terms of quality of life and morbidity associated with living with allergic disease. Similarly, early life eczema and egg allergy have been shown to be a risk for asthma, and possibly allergic rhino-conjunctivitis. We will assess the natural history of these conditions in an atopic population and will assess whether the benefits of the LEAP intervention extend to other atopic disease and other food allergens.

The nutritional consequences of consuming peanut in the LEAP Study has been published. The current study will help determine if these benefits are sustained beyond the first six years of life and after participants have been eating peanut *ad-libitum*.

We therefore aim to further investigate the clinical, immunological and nutritional safety findings of the LEAP and LEAP-On Studies. The findings will provide an opportunity to improve our understanding of how early-life introduction of peanuts may promote the development of tolerance at 12 years of age and will serve as an additional safety evaluation of this nutritional intervention.

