## 3.3 STUDY DEFINITIONS

#### 3.3.1 Determination of Primary Peanut Allergy

Peanut allergy status will be determined by peanut challenge where possible. Peanut challenges are described in section 6.7. Participants meeting criteria for peanut oral allergy syndrome in the absence of primary peanut allergy as described in section 3.3.5 will not be considered peanut allergic.

Individuals consuming at least 2g of peanut protein without reaction on at least one occasion in the last year will be considered peanut tolerant.

If oral challenge is not possible and participants do not meet the above criteria for tolerance, peanut allergy status will be determined by an internally and externally validated novel peanut allergy prediction model, the manuscript for which is currently in preparation: *Developing a Prediction Model for Determination of Peanut Allergy Status in The LEAP Trio Study*; Sever ML, Calatroni A, Du Toit G, et al. The model was developed using data from the LEAP participants, and incorporates peanut wheal size (mm), peanut specific IgE (kU/L), IgG4:IgE Ratio and Ara h2 (kU/L). The model performs with high level of accuracy, and continues to perform reasonably well in the context of missing blood or skin prick data. This model replaces the previously specified algorithm for determination of peanut allergy status. The details of the prior algorithm are included in the Appendix 2 for historical reference.

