8.2.1.1. Computation of the Primary Endpoint

Peanut allergy status at V144 will be determined by peanut challenge where possible. Peanut challenges are described in protocol section 6.7. Participants meeting criteria for peanut oral allergy syndrome in the absence of primary peanut allergy as described in protocol section 3.3.5 will not be considered peanut allergic.

Individuals who report consuming at least 2 g of peanut protein without reaction on at least one occasion in the last year will be considered peanut tolerant.

If oral challenge is not possible and participants do not meet the above criteria for tolerance, peanut allergy status will be determined by an internally and externally validated novel peanut allergy prediction model, the manuscript for which is currently in preparation: Developing a Prediction Model for Determination of Peanut Allergy Status in The LEAP Trio Study; Sever ML, Calatroni A, Roberts G, et al. The model was developed using data from the LEAP participants, and incorporates peanut wheal size (mm), peanut specific IgE (kU/L), Ara h1 (kU/L), Ara h2 (kU/L) and Ara h3 (kU/L). The model performs with high level of accuracy, and continues to perform reasonably well in the context of missing blood or skin prick data. This model replaces the previously specified algorithm for determination of peanut allergy status. The V144 assessments with non-missing data will be used as independent variables in the peanut allergy prediction model to impute peanut allergy status. LEAP Participants who do not have an oral food challenge, do not meet the peanut consumption criteria for tolerance and do not have any of the assessments for the peanut allergy prediction model will not be included in the primary analyses of the primary endpoint.

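### SAP 8.2.1.4 and 8.4.6 relate immune markers to V144 allergy status without separating children whose status a model derived from those same markers

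*SAP*

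**What the plan says.** SAP 8.2.1.1 gives three routes to V144 status in LEAP participants.

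1. Challenge: "Peanut allergy status at V144 will be determined by peanut challenge where possible".
2. Reported intake: anyone who reports "consuming at least 2 g of peanut protein without reaction on at least one occasion in the last year will be considered peanut tolerant".
3. Where neither applies, "peanut allergy status will be determined by an internally and externally validated novel peanut allergy prediction model", using the V144 measurements that are available.

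The two documents describe the model's inputs differently. In SAP 8.2.1.1 it "incorporates peanut wheal size (mm), peanut specific IgE (kU/L), Ara h1 (kU/L), Ara h2 (kU/L) and Ara h3 (kU/L"). In Protocol 3.3.1 it "incorporates peanut wheal size (mm), peanut specific IgE (kU/L), IgG4:IgE Ratio and Ara h2 (kU/L").

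SAP 8.2.1.4 then plans: "Immunologic outcomes and other clinical outcomes will be summarized and plotted to explore the relationships between the change or stability in the peanut allergy status". It does not name the immunologic outcomes, exclude the model's inputs, limit status to challenge results or flag model-assigned children. The last paragraph of SAP 8.4.6 repeats the plan in almost the same words.

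The analysis just before it is stricter. SAP 8.2.1.3 takes V72 status from the LEAP-On challenge, and only Consumers "who also have a determinant outcome in the V144 peanut oral food challenge will be included in the analysis". SAP 8.3.9.1 checks the model against challenges and reported intake, but nothing carries that result into 8.2.1.4.

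**The concern.** A child placed in the allergic group because wheal and IgE were high will, when plotted, show high wheal and IgE. That is the classification rule, not a finding about allergy. The question matters most in the allergic groups: they are small, and allergic labels in unchallenged children have no other source.

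Model assignment may also fall unevenly. Protocol 6.2.2 rules out a home challenge for any child at risk of a reaction. One of the risk criteria in Protocol 6.7.1 is itself a peanut wheal above 2 mm with no known ingestion. Telephone visits (Protocol 6.2.3) include no challenge. The intake rule takes tolerant children out of the model's reach. Model labels may therefore gather among the children whose immune profile is of interest.

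At stake is the reading of an exploratory display. Markers that feed the model could look more closely tied to new or persistent allergy than they are.

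**Working it through.** **Which labels are circular**

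| Route to V144 status | Possible result | Uses V144 wheal or IgE? |
|---|---|---|
| Food challenge | allergic or tolerant | not as the outcome criterion |
| Reported intake of at least 2 g | tolerant only | no |
| Prediction model | allergic or tolerant | yes |

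The circularity is direct for wheal, peanut IgE and Ara h2, which are on both lists. It is direct for Ara h1 and Ara h3 if the SAP list applies, and for the IgG4:IgE ratio if the protocol list applies. For other markers, such as Ara h6 or the cellular assays, it acts only through their correlation with the inputs.

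**Planning figures (Protocol 9.3)**

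There are 311 avoiders and 319 consumers eligible. With 80% enrolled, that is 248.8 and 255.2 children. The assumed allergy rates are 15% and 6%.

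Reproducing the stated power of 91%:
- Pooled rate = (37.32 + 15.31)/504 = 0.1044
- SE under no difference = √[0.1044 × 0.8956 × (1/248.8 + 1/255.2)] = 0.02725
- SE under the alternative = √[0.15 × 0.85/248.8 + 0.06 × 0.94/255.2] = 0.02708
- Power = Φ[(0.09 − 1.96 × 0.02725)/0.02708] = Φ(1.35) = 91.2%

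The planning basis is therefore sound. It implies 37.3 + 15.3, or about 53, allergic children at V144. The consumer rate was 4.8% at V72 (Protocol 1.1), so the net rise to 6% is 255.2 × 0.012, or about 3 children.

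**Illustration A: one marker, model labels more common among allergic children**

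All inputs are assumptions, because the documents do not give the model-assigned share.
- 400,000 simulated children, 10.5% truly allergic.
- The marker is N(0,1) in tolerant and N(μ,1) in allergic children, with μ = √2 × Φ⁻¹(AUC).
- The model calls a child allergic above the 89.5th percentile.
- Column heads give the shares of truly allergic / truly tolerant children who are model-assigned.

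| True AUC | 25% / 5% | 50% / 10% | 75% / 10% |
|---|---|---|---|
| 0.50 | 0.54 | 0.60 | 0.69 |
| 0.70 | 0.73 | 0.78 | 0.84 |
| 0.85 | 0.87 | 0.90 | 0.93 |
| 0.95 | 0.96 | 0.97 | 0.98 |

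A plot shows the gap between group means more directly than an AUC. At a true AUC of 0.85 the true gap is 1.47 SD and the displayed gap is 1.59, 1.74 or 1.95 SD (8%, 18% or 33% wider). The first row is an extreme: it supposes a model built on a useless marker, whereas both documents call the model highly accurate.

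**Illustration B: model labels at random**

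Prevalence is 11% and the true AUC is 0.85, with the model assigning whichever status is more probable.
- One-marker model: 20% to 40% model-assigned gives 0.86 to 0.875.
- Five conditionally independent inputs, each with AUC 0.85: one input reads about 0.85 to 0.86 overall, and 0.87 among model-assigned children. The more the inputs are correlated, the closer that last figure moves to 1.00.

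**Spurious new cases**

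Suppose 62 of 250 consumers were model-assigned. At false-positive rates of 1.6% and 3%, spurious cases number 62 × 0.016 = 1.0 and 62 × 0.03 = 1.9. There would be fewer if some of the 62 were already allergic at V72. All three inputs are assumed.

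**The case against.** The strongest reply is that the plan already protects what matters. SAP 8.2.1.3 is where new allergy and persistent tolerance are formally compared in Consumers, and it uses challenge results. SAP 8.2.1.4 only summarises and plots under an exploratory heading, with no test or AUC planned for that display. SAP 8.3.9.1 will bring model error to light. All of this stands, and it keeps the point modest. It leaves untouched the 8.2.1.4 display itself, which also covers Avoiders and mixes the three routes without a mark.

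Four stronger readings are tempting, and the documents do not support them.

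- *All unchallenged children are circular.* Those tolerant by reported intake are classified without wheal or IgE.
- *Each marker separates model-assigned children perfectly.* That holds for the model's score or a one-marker model. The documents describe four or five inputs.
- *The plan's IgG4 conclusions rest on this analysis.* Protocol 1.2 does say: "The longer-term trajectory of IgG4, and clinical relevance thereof, will become apparent after the determination of peanut allergy at 12 years of age". That is background and does not point to 8.2.1.4. The longitudinal immunoglobulin analysis in SAP 8.3.4.1 compares arms and visits, not allergy status. IgG4 enters the model only through the ratio on the protocol's list.
- *Restricting to challenged children cures the problem.* If likely-allergic children are challenged less often, that set is itself selected. Keeping reported-intake children in it would make this worse: unchallenged tolerant children would stay and every unchallenged allergic child would go.

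**Conclusion.** The point holds for SAP 8.2.1.4 and the closing paragraph of SAP 8.4.6. Where V144 status came from the model, its association with the model's inputs is partly built in, and the plan neither separates nor flags these children.

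The size cannot be derived from the documents. It depends on the model-assigned share by true status, the correlation among inputs and the accuracy of the model, none of which is given. Across the illustrations a true AUC of 0.85 reads from about 0.85 to 0.93, and a very accurate marker hardly moves (0.95 reads 0.96 to 0.98). One or two misassigned children would be noticeable against a net rise of about 3 in consumers, but that comparison rests on assumed rates.

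A reader might infer that the co-primary result or the McNemar comparison is compromised. This point touches neither. It is worth correcting because the correction is nearly free, not because it threatens a main conclusion.

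**What to change.** In SAP 8.2.1.4 and 8.4.6:

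- Tabulate how V144 status was determined (challenge, reported intake, model), by arm and by status.
- Show each summary and plot twice: for challenge-determined status only, and for all children with model-assigned children under a separate symbol.
- State that the model's own inputs will not be interpreted as correlates of allergy within model-assigned children.
- Flag V60 and V72 statuses not based on a challenge in the same way. Protocol Appendix 2 describes an earlier algorithm, based on the one used in LEAP, that relied on skin-prick and IgE results.
- Flag challenge results reclassified as oral allergy syndrome, because Protocol 3.3.5 uses Ara h components for that decision.
- Reconcile the model inputs in Protocol 3.3.1 and SAP 8.2.1.1, so that it is clear which markers are directly affected.

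The cost is a few SAP sentences and one variable recording the source of status. The challenge-only version will have fewer children and may be selected, which is why both versions are needed.
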